9.4 STATISTICAL ANALYSES

9.4.1 GENERAL APPROACH

The effects of each nudge intervention relative to the control group and to each other will be tested using a four-level hierarchical model adjusted for multiple hypothesis testing.

9.4.2 ANALYSIS OF THE PRIMARY AND SECONDARY EFFICACY ENDPOINTS

Our primary outcome is the share of discharge prescriptions that were above the guideline for the respective procedure (see above for how guidelines were identified). Prescribing above guidelines is the outcome to which both nudges are linked (even though the descriptive norm nudge does not explicitly refer to guidelines) and thus a key measure of whether clinician behavior responds to the nudges. We define a prescription as being above guidelines if the morphine milligram equivalent (MME) quantity of opioids prescribed is above the ceiling for the procedure-specific guideline (guidelines range from zero to a ceiling). If no opioid is prescribed at discharge, we will code this as within guideline.

We will also analyze the following secondary outcomes to further understand the effects of the intervention.

- MMEs prescribed at discharge
- Days' supply of opioids prescribed at discharge
- Share of discharges where any opioid was prescribed
- Share of patients on opioids for greater than three months post-discharge
- Number of 30-day all-cause emergency department visits
- Number of 30-day all-cause hospitalizations
- Share of discharge opioid prescriptions above prescribing guidelines in the 12 months after the nudges end

Primary analysis

We will analyze outcomes at the level of the discharge using a four-level hierarchical linear model (HLM),[42] thus capturing the clustering inherent in the study design and data generating process. We will analyze outcomes at the patient level, and patients are nested within surgeons, who are nested within specialties, which are nested within hospitals. Both primary and secondary outcomes will follow this modeling structure. To improve the precision of our estimates, we will also include a set of observable patient covariates (X), surgeon covariates (Z), specialty covariates (U), and hospital covariates (W). For patient i , treated by surgeon p , in specialty s , at hospital h , we consider the following HLM formulation for continuous outcomes Y_{ipsh} :

$$Y_{ipsh} = \beta_0 + \beta_1 ARM1_{sh} + \beta_2 ARM2_{sh} + \gamma_{1h} ARM1_{sh} + \gamma_{2h} ARM2_{sh} + \omega_1 X_{ipsh} + \omega_2 Z_{psh} + \omega_3 U_{sh} + \omega_4 W_h + \gamma_h + \eta_{sh} + \varphi_{psh} + \varepsilon_{ipsh} \quad (1)$$

$ARM1_{sh}$ and $ARM2_{sh}$ are indicator variables for whether specialty s , at hospital h were assigned to intervention arm one or two respectively.

The key terms in the equation are β_1 and β_2 , the covariate-adjusted treatment effects of arms 1 and 2 relative to the control arm; β_1 answers research question 1 and β_2 answers research question 2. We will use an F-test to compare coefficients β_1 and β_2 to answer research question 3. Thus, the effect of each nudge is estimated relative to receiving no nudges and to the other nudge.

The model allows for the possibility that the treatment effect varies across hospitals, as captured by the random effects (γ_{1h}, γ_{2h}). Unexplained variation in each of the levels is captured by the random effects $\varepsilon_{ipsh}, \varphi_{psh}, \eta_{sh}$, and γ_h . We will initially model these six random effects as independent but will also investigate whether including a covariance structure across these components is appropriate. The coefficients ω_1, ω_2 , and ω_3 , capture the influence of the covariates at the patient, surgeon, and specialty respectively, and covariates will be mean centered as appropriate to aid in model

interpretation. Covariates may include but are not limited to the following: Level 1: patient age, patient sex, patient comorbidities, procedure type, length of operating time; Level 2: surgeon sex, year of surgeon's medical degree; Level 3: total volume of procedures within the specialty; Level 4: number of beds, urbanicity, proportion of patients on Medicaid. Given that the covariates will not change the estimate of the treatment effect (in expectation), only reduce unexplained variance, we will choose a final pool of covariates that we find to be predictive the primary outcome. Model estimates of the treatment effects will adjust standard errors for clustering due to the due to clustered assignment of the interventions.

For binary outcomes, we implement a hierarchical generalized linear model by including a logit link for Equation (1). Note that the Level 1 error term ε_{ipsh} is also eliminated. The concatenated model for all four levels with a binary outcome then reduces to:

$$\text{logit}(Y_{ipsh}) = \beta_0 + \beta_1 \text{ARM1}_{sh} + \beta_2 \text{ARM2}_{sh} + \gamma_{1h} \text{ARM1}_{sh} + \gamma_{2h} \text{ARM2}_{sh} + \omega_1 X_{ipsh} + \omega_2 Z_{psh} + \omega_3 U_{sh} + \omega_4 W_h + \gamma_h + \eta_{sh} + \varphi_{psh} \quad (2)$$

In the binary outcome version, the parameters β_1 and β_2 again identify the treatment effects of arms 1 and 2 relative to the control arm, with interpretation of these parameters adjusted relative to the link function implemented.

Longitudinal analysis

In addition to assessing the treatment effect averaged over the entire 12-month period, we will also analyze treatment effects by month to assess how the treatment effect evolves over time. For this analysis, we will interact study month indicators with the treatment assignment indicators.

Persistence analysis

We will conduct a secondary analysis to examine whether nudge effects persist once the nudges are discontinued. The data will include the RCT data analyzed in the model above, but also data collected for one year post-intervention (the "persistence period"). The analysis model above will be modified by adding an indicator for the RCT period versus persistence period plus interaction terms for period and each nudge to the model. The statistical significance of these interaction terms will be used to assess whether the treatment effect significantly differs post-RCT.

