3 OBJECTIVES AND ENDPOINTS

OBJECTIVES	ENDPOINTS
Primary	
To test the effectiveness of two behavioral nudges, one based on peer behavior and one based on best practice guidelines, in reducing the share of discharge opioid prescriptions above procedure-specific prescribing guidelines	Share of discharge opioid prescriptions above prescribing guidelines
Secondary	
To test the effectiveness of two behavioral nudges, one based on peer behavior and one based on best practice guidelines, in reducing the morphine milligram equivalent quantities and days' supply prescribed at discharge	Morphine milligram equivalents (MMEs) prescribed at discharge, days' supply of opioids prescribed at discharge
To test the effectiveness of two behavioral nudges, one based on peer behavior and one	Share of discharges where any opioid was prescribed

OBJECTIVES	ENDPOINTS
based on best practice guidelines, in reducing the share of discharges with any opioids prescribed	
To test the long-term effects on patients of two behavioral nudges, one based on peer behavior and one based on best practice guidelines	Share of patients on opioids for greater than 3 months post-discharge
To test the persistence of the effectiveness of two behavioral nudges, one based on peer behavior and one based on best practice guidelines, in reducing the share of discharge opioid prescriptions above procedure-specific prescribing guidelines	Share of discharge opioid prescriptions above prescribing guidelines in the 12 months after the nudges stop being delivered
To test the safety of two behavioral nudges, one based on peer behavior and one based on best practice guidelines	Number of 30-day all-cause emergency department visits, number of 30-day all-cause hospitalizations

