9 STATISTICAL CONSIDERATIONS

9.1 STATISTICAL HYPOTHESES

The null hypotheses are that (1) $\beta_1 = 0$, (2) $\beta_2 = 0$, and (3) $\beta_1 = \beta_2$ in the hierarchical linear model

$$Y_{ipsh} = \beta_0 + \beta_1 ARM1_{sh} + \beta_2 ARM2_{sh} + \gamma_{1h} ARM1_{sh} + \gamma_{2h} ARM2_{sh} + \omega_1 X_{ipsh} + \omega_2 Z_{psh} + \omega_3 U_{sh} + \omega_4 W_h + \gamma_h + \eta_{sh} + \varphi_{psh} + \varepsilon_{ipsh}, \quad (1)$$

where i is the patient treated by surgeon p in specialty s at hospital h , $ARM1_{sh}$ and $ARM2_{sh}$ are indicator variables for whether specialty s at hospital h were assigned to intervention arm one or two respectively, X is a set of patient covariates, Z is a set of surgeon covariates, U is a set of specialty covariates, and W is a set of hospital covariates.

The alternative hypotheses are that (1) $\beta_1 \neq 0$, (2) $\beta_2 \neq 0$, and (3) $\beta_1 \neq \beta_2$.

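### The safety endpoints are judged by the efficacy test of zero effect, apparently multiplicity-adjusted, with no interval-based criterion, so a non-significant result would not show safety

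*Combined protocol and SAP*

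**What the plan says.** Section 3 sets a secondary objective, "To test the safety of two behavioral nudges, one based on peer behavior and one based on best practice guidelines", with these endpoints: "Number of 30-day all-cause emergency department visits, number of 30-day all-cause hospitalizations". Section 9.4.2 repeats both in its list of secondary outcomes and states: "Both primary and secondary outcomes will follow this modeling structure".

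That structure is the four-level hierarchical model of section 9.1. Its null hypotheses are no effect of each nudge against control and no difference between the nudges; the alternatives are two-sided. Section 9.4.1 says the effects are "tested using a four-level hierarchical model adjusted for multiple hypothesis testing". It names neither the method of adjustment nor the family of tests, and it makes no exception for safety. Section 9.4.2 gives a linear model for continuous outcomes and a logit model for binary ones, and nothing for counts.

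A second safety track exists. Sections 8.2 and 9.4.3 plan monthly reports of numerator, denominator and ratio by arm, which go to the DSMB twice a year. They cover ED visits and opioid refills.

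**The concern.** An efficacy test asks whether there is enough evidence to claim an effect. Failing to reject a zero effect means only that the data did not exclude zero; the same data may be compatible with a sizeable increase in ED visits or admissions. To support a statement that the nudges are safe, the analysis has to show how large an increase remains plausible, which is a question about the upper confidence limit. The plan sets no such criterion.

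Multiplicity adjustment protects against false claims of benefit. Applied to harm, it raises the evidence needed to flag an increase. The efficacy result is not affected. What is at stake is whether the safety objective can be answered at all, and more so for hospitalization, where the secondary-outcome test is the only comparison between arms that the plan specifies. The amendment history (section 10.3) shows that a patient pain survey was dropped, so few other harm measures remain.

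**Working it through.** **1. Is there a planned figure for safety?** No. The only power figure (section 9.2) is for medication dose: a detectable effect of 0.347 SD (R² = 0.25) or 0.305 SD (R² = 0.5) at alpha 0.05/2. It cannot be reproduced, because the numbers of providers and patients per service line are not given. Nor does it carry over to ED visits, because it depends on a provider ICC of 0.337 estimated for dose.

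**2. Cost of the adjustment, with few assumptions.** For a normal test, the loss from moving alpha from 0.05 (z = 1.960) to 0.05/2 (z = 2.241) depends only on the unadjusted power: 80% becomes 71%, 50% becomes 39%, and 30% becomes 21%.

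**3. The same cost on an assumed grid.** The documents give no safety event rate, safety ICC or discharge count, so these are assumptions: control rate p of 5% or 10%, n of 3,000 or 10,000 discharges per arm, ICC of 0.005 or 0.01. About 19 specialty clusters per arm follow from 19 hospitals with up to three specialties each and three arms.

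- SE = sqrt(2p(1−p)·DE/n), with DE = 1 + (n/19 − 1)·ICC
- 95% half-width = 1.96·SE
- Power for a 20% relative rise = Φ(0.2p/SE − z)

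Example with p = 0.05, n = 3,000, ICC = 0.01:

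- DE = 1 + (157.9 − 1)(0.01) = 2.569
- SE = sqrt(2 × 0.0475 × 2.569/3,000) = 0.00902
- 0.2p/SE = 0.010/0.00902 = 1.109
- Power = Φ(1.109 − 1.960) = 19.7% at 0.05, and Φ(1.109 − 2.241) = 12.9% at 0.05/2

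| Rate | n per arm | ICC | DE | Half-width (points) | Power at 0.05 | Power at 0.05/2 | Loss (points) |
|---|---|---|---|---|---|---|---|
| 5% | 3,000 | 0.005 | 1.784 | 1.47 | 26.4% | 18.1% | 8.3 |
| 5% | 3,000 | 0.01 | 2.569 | 1.77 | 19.7% | 12.9% | 6.8 |
| 5% | 10,000 | 0.005 | 3.627 | 1.15 | 39.9% | 29.5% | 10.4 |
| 5% | 10,000 | 0.01 | 6.253 | 1.51 | 25.4% | 17.3% | 8.1 |
| 10% | 3,000 | 0.005 | 1.784 | 2.03 | 48.9% | 37.9% | 11.0 |
| 10% | 3,000 | 0.01 | 2.569 | 2.43 | 36.4% | 26.4% | 10.0 |
| 10% | 10,000 | 0.005 | 3.627 | 1.58 | 69.7% | 59.3% | 10.4 |
| 10% | 10,000 | 0.01 | 6.253 | 2.08 | 47.0% | 36.1% | 10.9 |

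The loss is 7 to 11 points throughout. The half-width is 1.2 to 2.4 points, or 16% to 35% of the control rate. On this grid, a non-significant result could leave an increase of that order or more unexcluded.

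**4. How firm is the absolute power?** Not firm. On the same grid at 0.05/2, power is 13-59% for a 20% rise, 28-93% for 30%, and 49% to over 99% for 40%. With an ICC of 0.001-0.002 and 10,000 per arm, power for a 20% rise is 51-94%. The formula also ignores the blocking by hospital and the covariates.

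**5. Would pooling the nudges help?** The variance factor for one nudge against control is 2, and for both pooled it is 1.5. The SE therefore shrinks by sqrt(1.5/2) = 0.866, about 13%. If only one nudge does harm, the pooled effect is halved and the expected z falls to 0.5/0.866 = 58% of that arm's own comparison.

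**The case against.** The strongest reply is that safety does not rest on the adjusted test alone. ED visits are also reported monthly by arm, with no test and no adjustment, to a DSMB that can recommend stopping the intervention (section 7.1). Section 10.1.6 says the data elements the board needs will be defined under its charter, which is not among the documents. This stands for ED visits and refills. But the reports as described carry no intervals, no allowance for clustering and no threshold, and they leave out hospitalization, which is half of the safety objective.

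A reader might go further than the evidence in three ways:

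- That a relevant increase would most likely be missed. This rests wholly on assumed rates, ICCs and patient numbers, and on what size of rise counts as relevant. Step 4 shows power from low to nearly certain.
- That the investigators will report a non-significant result as safety. Nothing in the plan says so; section 9.4.2 speaks of estimating each nudge's effect.
- That the adjustment is the main problem. It costs some power, but patient numbers, clustering and the missing criterion matter more. Its reach to the safety endpoints is inferred from one general sentence, and the only adjusted level stated anywhere is 0.05/2, in the power calculation.

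**Conclusion.** The point holds in a limited form. The two endpoints of the safety objective go through two-sided tests of zero effect, with no interval-based criterion, so non-significance cannot answer that objective. This follows from the text and needs no assumption about rates. If the general adjustment applies to them, as the wording suggests, it costs about 7 to 11 points of power for a 20% relative rise at alpha 0.05/2, under assumed rates of 5-10%, 3,000-10,000 discharges per arm and an ICC of 0.005-0.01. Whether a given increase would be detected cannot be settled from the documents. The gap is widest for hospitalization, which the descriptive DSMB reports do not cover. The change is worth making because it is cheap; it does not bear on the efficacy conclusions.

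**What to change.** - In 9.4.1 and 9.4.2, state that 30-day ED visits and hospitalizations lie outside the multiplicity-adjusted family.
- For each nudge versus control, report the rate difference and the rate ratio with unadjusted 95% confidence intervals, from a log-link count model with the same clustering. Show pooled nudges versus control as a supplementary contrast only, for the reason in step 5.
- Base the safety conclusion on the upper confidence limit, against a criterion agreed with the DSMB before unblinding, and not on a p-value above alpha.
- Add hospitalization to 8.2 and 9.4.3 so that they match section 3. Section 8.1 already collects inpatient visits within 30 days of discharge, so no new data are needed.

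The cost is SAP wording and one agreement with the DSMB. A safety claim may become harder to make. Four unadjusted intervals (two nudges, two endpoints) also carry a chance of at most 4 × 2.5% = 10% that at least one points to harm when there is none, which is an acceptable price for a harm question.

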9.2 SAMPLE SIZE DETERMINATION

Statistical power to identify effects of the nudges was examined using recent past data from the participating hospitals. We estimated design parameters required by the PowerUpR package in R software,⁴⁸ which provides the capability to estimate statistical power for randomized block clustered designs. Examining medication dose, input parameters for the calculation included unconditional intracluster correlations (ICC) for the hospital (ICC=0.005), service line (ICC=0.039), and provider (ICC=0.337) levels; the number of service line groups (up to three per hospital); the number of providers by service line expected to participate in the study; and number of patients per service line. The ICCs were empirically determined from our preliminary data. We assumed that covariates informative of the dosage would explain between 25 percent and 50 percent of the dosage variation at each of the patient, provider, and service line levels (i.e., R^2 between 0.25 and 0.50). We derived statistical power, assuming one third of the service line groups within hospital will be randomly assigned to each study arm (two treatment and one control). We computed power for pairwise comparison of each of the two nudge arms versus the no nudge arm and adjusted our alpha level to account for multiple comparisons (alpha=0.05/2). We will have 80% power to detect significant differences between the intervention conditions of at least a minimum detectable effect size (MDES) = 0.347 standard deviations (SDs) when $R^2=0.25$, while $R^2=0.5$ would yield a MDES of 0.305.

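### The persistence test rests on period-by-nudge terms in a model with only time-constant random effects, so its standard errors may be substantially understated unless a cluster-robust variance is specified to cover them

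*Combined protocol and SAP*

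**What the plan says.** Section 9.4.2 sets out a four-level model with patients in surgeons, surgeons in specialties and specialties in hospitals. Its random terms are a hospital effect, two hospital-specific arm effects, a specialty effect, a surgeon effect and the patient-level residual, which is dropped for binary outcomes. None carries a time index. The plan states that "Unexplained variation in each of the levels is captured by the random effects" and that "The model allows for the possibility that the treatment effect varies across hospitals". On correlation among the terms it says: "We will initially model these six random effects as independent but will also investigate whether including a covariance structure across these components is appropriate". That covariance structure concerns the same six terms.

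Two further analyses in the same section build on this model:

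- **Persistence.** Data from the year after the nudges are added, and the model is changed by "adding an indicator for the RCT period versus persistence period plus interaction terms for period and each nudge to the model". The decision rule is: "The statistical significance of these interaction terms will be used to assess whether the treatment effect significantly differs post-RCT".
- **Longitudinal.** For effects by month, "we will interact study month indicators with the treatment assignment indicators". No significance rule is attached.

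Under the primary analysis the plan also says: "Model estimates of the treatment effects will adjust standard errors for clustering", and gives clustered assignment as the reason. It does not say whether this means a robust variance or only the random effects. It mentions no small-sample correction and does not say whether the time-by-nudge terms are covered.

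**The concern.** A period-by-nudge term compares the same surgeons and the same specialty units in two periods. A constant surgeon, specialty or hospital effect cancels from that comparison. The model-based error that remains is essentially patient-level noise divided by the number of discharges. Any change in a surgeon's or department's prescribing level from one year to the next is shared by all of that unit's discharges, and the model has no term for it.

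Persistence is a listed secondary objective, and it is to be settled by the p-values of exactly these terms. If they are anticonservative, the trial could report that a nudge effect faded or grew after the emails stopped when the data show only ordinary year-to-year movement in at most 19 × 3 = 57 randomised units.

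**Working it through.** **Is there a figure in the plan to reproduce?** No. Section 9.2 gives a minimum detectable effect for the main arm comparison only. It cannot be reproduced, because the numbers of surgeons and patients per cluster are not stated. Nothing is given for the interaction terms.

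**Inputs from the plan.** Section 9.2 gives "hospital (ICC=0.005), service line (ICC=0.039), and provider (ICC=0.337) levels", estimated for medication dose. The residual share by subtraction is 1 − 0.005 − 0.039 − 0.337 = 0.619. The hospital share is small and is left out below.

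**Assumed inputs.** J surgeons per cluster (3.5 to 8); n discharges per surgeon per year (20 to 40); w, the share of surgeon and specialty variance that is specific to a period (0 to 0.20); a two-sided nominal 5% test. The documents give none of these for the persistence analysis.

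**Formulas, per cluster and period.**

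- True variance: 0.039w + 0.337w/J + 0.619/(Jn)
- Model-based variance: 0.619/(Jn), or (0.619 + 0.376w)/(Jn) if the residual absorbs the omitted variance (0.376 = 0.039 + 0.337)
- SE ratio = √(true/model); rejection rate = 2[1 − Φ(1.96/ratio)]

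The difference over two periods and two arms multiplies both variances by 4 and divides both by the number of clusters per arm, so the ratio does not depend on the number of clusters.

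**Worked cases, w = 0.05.**

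- J = 3.5, n = 20: true = 0.00195 + 0.00481 + 0.00884 = 0.01561; model = 0.00884; ratio = 1.33; rejection 14.0%. With an absorbing residual, the model variance is 0.00911, the ratio 1.31 and rejection 13.4%.
- J = 8, n = 40: true = 0.00195 + 0.00211 + 0.00193 = 0.00599; model = 0.00193; ratio = 1.76; rejection 26.5%. With an absorbing residual, 25.8%.

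**Rejection rates for the persistence term** (fixed residual / absorbing residual):

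| w | J = 3.5, n = 20 | J = 8, n = 40 |
|---|---|---|
| 0 | 5.0% / 5.0% | 5.0% / 5.0% |
| 0.01 | 6.8% / 6.7% | 10.0% / 9.9% |
| 0.05 | 14.0% / 13.4% | 26.5% / 25.8% |
| 0.10 | 21.8% / 20.4% | 39.0% / 37.6% |
| 0.20 | 33.1% / 30.3% | 52.2% / 49.8% |

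**Simulation check.** With 19 clusters per arm, J = 6, n = 50 and 4,000 runs, model-based rejection was 4.0%, 10.9%, 27.3%, 40.6% and 52.1% at w = 0, 0.01, 0.05, 0.10 and 0.20. With standard errors computed at the randomised-cluster level it was 4.0%, 5.5%, 5.2%, 4.6% and 4.9%.

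**Monthly terms.** The same yearly counts are 1.7 to 3.3 discharges per surgeon-month. For a single month contrast at w = 0.05, the fixed-residual formula gives 5.7% (J = 3.5, n = 20/12) to 7.1% (J = 8, n = 40/12); the absorbing version gives 5.4% to 6.6%. In simulation (J = 6, 2,000 runs), a joint 11-df test of the month terms at w = 0.05 rejected 7.4% of the time with 2 discharges per surgeon-month and 10.9% with 4. Four per month is 48 a year, above the range assumed here.

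**The case against.** The strongest reply is that the plan already deals with clustering. The adjustment sentence ties the standard errors to clustered assignment, and sections 4.1 and 6.3 fix the assigned unit as the specialty within a hospital. The persistence model is described as a modification of the model set out before it, and section 9.4.2 says that secondary outcomes follow the same structure. If the sentence means a robust variance at that unit, and it carries over, the simulation shows that the problem largely disappears. This reading is possible, but the text does not commit to it. The sentence speaks of the treatment effects, which section 9.4.2 defines as β1 and β2, and it could describe no more than the random effects themselves. An analyst could follow the plan to the letter and report purely model-based interaction p-values.

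A second reply is that no document gives a between-period correlation, a number of surgeons per cluster or a number of discharges per surgeon, and that the ICCs are for dose while the persistence endpoint is a binary share analysed with a logit link. All of that stands. It makes the size of the problem conditional, and with no drift there is no inflation at all.

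A reader might infer that the standard errors are certain to be far too small, and equally so in the monthly and the persistence models. The documents do not support that. The drift is unknown, the clustering sentence may supply the cure, and at the assumed discharge counts and 5% drift the monthly inflation is slight. The monthly analysis also has no significance rule attached.

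**Conclusion.** The gap is real and mainly concerns the persistence analysis. The plan adds only fixed period terms to a model with time-constant random effects, decides persistence on their significance, and does not say that a cluster-robust variance applies to them. If the standard errors are purely model-based and 5% of the surgeon and specialty variance is period-specific, they are too small by a factor of about 1.3 to 1.8. Drift of only 1% already moves the nominal 5% test to about 7-10%.

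These figures rest on the assumed cluster sizes and drift, on the dose ICCs, and on a linear, balanced calculation without covariates. They illustrate sensitivity and do not predict this trial's error rate. It would also be wrong to infer that the main result is compromised: the 12-month arm comparison contains no period contrast and is unaffected.

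**What to change.** For the persistence model, write one of the following into section 9.4.2:

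1. Add random surgeon-by-period and specialty-at-hospital-by-period effects.
2. State that the clustering adjustment is a sandwich variance clustered on the randomised specialty-within-hospital unit, with a small-sample correction, and that it applies to the period-by-nudge tests.

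For the monthly model, use the same cluster-robust variance. Surgeon-by-month random effects should not be required, because they may not be estimable with so few discharges per cell.

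The cost is a few lines of wording, some extra modelling work, and wider confidence intervals for the interaction terms. No new data are needed.
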